We will recruit up to 10 subjects with a goal of 8 completers. Study candidates will be screened for inclusion and exclusion criteria by any member of the study team. Those who meet criteria and consent to the study will be enrolled. If no consent provided, the patient will not be enrolled and the reason for their non-participation included with the date of screening.

Eligibility Criteria

Inclusion Criteria

- Provide consent to participate in the study
- Individuals of either sex, 21-85~~9~~ years of age
- Clinically defined Restless Leg Syndrome, and problematic augmentation currently on dopaminergic treatment.
- Subjects with reproductive capability including all males and women of child-bearing potential (WOCBP) must agree to practice continuous abstinence or adequate contraception methods (appropriate double barrier method or oral, patch, implant, or injectable contraception) from as soon as feasible during screening period until at least 30 days after the last dose (i.e., intermittent abstinence based on “rhythm”, temperature monitoring, or other means of timing is not acceptable)

Exclusion Criteria

- Current use of Opioid medications
- Clinical relevant depression or other medical problems that in the opinion of the investigator would not allow for safe completion of the protocol.
- Suicidal ideation
- History of epilepsy
- Current MAO inhibitors
- History of hepatic or renal impairment
- Women who are pregnant or breastfeeding

Study Procedures

Our aim is to determine the mechanism of dopaminergic induced augmentation and if a D1 antagonist drug can improve augmentation symptoms. Subjects will be randomized to Ecopipam or placebo for 5 weeks/arm in two periods with a 2-week washout period in between. Total time for subject participation is

approximately 13 weeks.

Medical History

The history will center on risk factors and symptoms or disorders relevant to neurological disorders.

Physical and Neurological Examinations

Brief standard neurological examinations will be done similar to that of a normal clinic visit. Laboratory assessments of serum chemistry and a 12-lead ECG will be conducted on the first day (before initiating treatment) and the last day of treatment of each crossover phase (i.e. Ecopipam or placebo).

At each Visit subjects will undergo:

- Verification of continued trial participation
- Assessment of overall wellness with query for adverse events and safety reporting

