- Clinical Global Impressions and safety calls at week 1 and 3 of each arm, and 1 week after withdrawal) of each arm.
- Completion of following instruments:
 - International RLS Rating Scale,
 - Augmentation Severity Rating Scale,
 - Epworth Sleep Scale,
 - Hamilton Depression Scale,
 - MOS Sleep Scale,
 - Fatigue Severity Scale, and
 - Montreal Cognitive Assessment
 - Columbia Suicide Assessment Scale.
 - Vital signs and examination
- Education on and/or review of the 24-hour RLS Symptom diary to be kept just prior to starting each arm and just before ending each arm. Analysis will be last observation carried forward.

Concurrent Medications for RLS

The following medications are allowed dopamine agonists (pramipexole, ropinirole, rotigotine)
The following medications are prohibited: dopamine antagonists, anti-histaminergic medications. In addition, Ecopipam has been shown a competitive inhibitor for CYP2D6 at nanomolar concentrations, and as such, the use of strong CYP2D6 inhibitors (i.e. Fluoxetine, Paroxetine, Bupropion, Quinidine, Cinacalcet and ritonavir) are prohibited.

Schedule of Events:

Study procedures (Per patient)	Baseline Screening Visit: Day -14 to 0	Visit 1: Day 0	Phone Call 1: Day 8	Visit 2: Day 15	Phone Call 2: Day 22	Visit 3: Day 36	Phone Call 3: Day 43	Visit 4: Day 50	Phone Call 4: Day 57	Visit 5: Day 65	Phone Call 5: Day 72	Visit 6: Day 84	Phone Call 6: Day 91
Informed consent	X												
Inclusion/exclusion criteria	X												
Demographic data	X												
Medical history	X												
Prior and/or concomitant medication review	X	X	X	X	X	X	X	X	X	X	X	X	X
Physical examination/Neurological exam	X			X		X		X		X		X	
Vital signs	X			X		X		X		X		X	
12-Lead ECG	X					X						X	
Urine pregnancy test (WOCBP)	X					X						X	
Serum Chemistry	X					X						X	
International RLS Rating Scale (IRLS Scale)		X		X		X		X		X		X	
Body weight and height		X		X		X		X		X		X	
Augmentation Severity Rating Scale	X	X		X		X		X		X		X	
Epworth Sleep Scale		X		X		X		X		X		X	
Hamilton Depression Scale		X		X		X		X		X		X	
MOS Sleep Scale		X		X		X		X		X		X	
Montreal Cognitive Assessment (MoCA)		X		X		X		X		X		X	
Fatigue Severity Scale		X		X		X		X		X		X	
Columbia-Suicide Severity Rating Scale (C-SSRS)		X		X		X		X		X		X	
Clinical Global Impressions (CGI)		X	X	X	X	X	X	X	X	X	X	X	X
Dispense 24-hour RLS Symptom diary	X							X					
Review of 24-hour RLS symptom diary		X		X		X		X		X		X	
Study drug dispensation		X						X					
Adverse Events		X	X	X	X	X	X	X	X	X	X	X	X

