During the study, the Investigator and study team will be responsible for monitoring, collecting, following-up on, and reporting AEs and SAEs, as detailed in this section of the protocol. Adverse events will be reported by the subject (or, when appropriate, by a caregiver, surrogate, or the subject's legally acceptable representative) according to the definition below. Only adverse events associated with the research component of trial participation will be captured, examples include but are not limited to: somnolence, headache, insomnia.

The stopping rules for this trial will be determined by the Sponsor Investigator, Houston Methodist Hospital &/or Houston Methodist Research Institute, and/or HMRI Institutional Review Board. The Principal Investigator may withdraw a subject for their safety and welfare. Participants will be withdrawn at either 3x ULN for AST/ALT, kidney function changes from baseline as determined by BUN/Creatinine or when unintended pregnancy occurs.

Event Monitoring Definitions

Adverse Event (AE): An adverse event (AE) is any untoward medical occurrence associated with the use of a drug in humans, whether or not considered drug related. An adverse event can therefore be any unfavorable and unintended sign (including an abnormal laboratory finding), symptom, or disease temporally associated with the use of a drug and does not imply any judgment about causality. An adverse event can arise with use of any drug or medicinal product. AEs are to be reported to the IRB per IRB policy and to the sponsor at the time of annual reporting.

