Serious Adverse Event (SAE): A serious adverse event (SAE) is any untoward medical occurrence that occurs irrespective of study treatment assignment, if it satisfies any of these criteria: results in death; is life-threatening; requires inpatient hospitalization or prolongs existing hospitalization; results in persistent or significant disability or incapacity or substantial disruption of the ability to conduct normal life functions; or if the event is a congenital anomaly or birth defect. Important medical events that may not result in death, be life-threatening, or require hospitalization may be considered serious when, based upon appropriate medical judgment, they may jeopardize the patient or subject and may require medical or surgical intervention to prevent one of the outcomes listed in this definition. SAEs are to be reported to the IRB per IRB policy and to the sponsor at the time of IRB reporting for further reporting to the FDA.

Assessment of Intensity: The Investigator will make an assessment of intensity for each AE and SAE reported during the study. The assessment will be based on the Investigator's clinical judgment. The intensity of each AE and SAE recorded in the subject record should be assigned to one of the following categories:

- Mild: An event that is easily tolerated by the subject, causing minimal discomfort and not interfering with everyday activities.
- Moderate: An event that is sufficiently discomforting to interfere with normal everyday activities.
- Severe: An event that prevents normal everyday activities.

Relationship to Study Drug - Assessment of Causality: The Investigator is obligated to assess the relationship between study drug and the occurrence of each AE/SAE. The Investigator will use clinical judgment to determine the relationship. Alternative causes, such as natural history of the underlying diseases, concomitant therapy, other risk factors, and the temporal relationship of the event to the study drug will be considered and investigated. The Investigator will assess causality based on the following definitions:

- Not Related (the AE was more likely explained by causes other than the study treatment).
- Related (the study treatment and AE were closely related in time and the AE may be explained by exposure to study product: e.g., known pharmacological effect or recurrence on re-challenge).

Participant Compensation

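### No pregnancy test is scheduled at either dispensing visit or between Day 36 and Day 84, although pregnancy requires withdrawal, and scheduled contact ends before the 30-day contraception commitment does

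*Protocol*

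**What the plan says.** - **Eligibility Criteria.** Pregnancy is an exclusion. All males and women of child-bearing potential must agree to contraception "from as soon as feasible during screening period until at least 30 days after the last dose".
- **Safety Monitoring of Subjects.** The list of reasons for withdrawing a participant ends with "or when unintended pregnancy occurs".
- **Schedule of Events.** The row "Urine pregnancy test (WOCBP") is marked at Screening (Day -14 to 0), Visit 3 (Day 36) and Visit 6 (Day 84). Drug is dispensed at Visit 1 (Day 0) and Visit 4 (Day 50). The eligibility check is marked at Screening only. The last column is "Phone Call 6: Day 91".
- **Study Procedures.** The design sentence reads "Subjects will be randomized to Ecopipam or placebo for 5 weeks/arm in two periods with a 2-week washout period in between", and participation is given as "approximately 13 weeks". Chemistry and ECG are to be done before treatment starts and on the last treatment day of each crossover phase. Calls include one "and 1 week after withdrawal) of each arm".
- **Event Monitoring Definitions.** The criteria for a serious adverse event include "or if the event is a congenital anomaly or birth defect".

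**The concern.** A withdrawal rule needs some scheduled means of finding the event that triggers it. In Period 2 the only pregnancy test comes at the end of dosing, when withdrawal can prevent little or no further exposure. The exclusion of pregnant women is not scheduled for re-checking before the second course of blinded drug is handed out.

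After the last dose, participants remain bound by a contraception undertaking for weeks in which nobody is scheduled to ask about it. Tolerability is one of the study's stated purposes, and these are gaps in how one safety event would be found. They do not affect any efficacy comparison.

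**Working it through.** **Reproducing the stated duration.** Day 0 to Day 91 is 91/7 = 13.0 weeks, or 5 + 2 + 5 + 1 weeks, the last being the week up to the final call. This matches the protocol's figure and confirms Day 91 as the planned end of contact. Screening can add up to 14 days.

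**Tests against dispensing, from the Schedule of Events.**

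| Dispensing | Previous test | Gap | Next test | Gap |
|---|---|---|---|---|
| Day 0 | Screening, Day -14 to 0 | 0 to 14 days | Day 36 | 36 days |
| Day 50 | Day 36 | 50 - 36 = 14 days | Day 84 | 84 - 50 = 34 days |

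The interval between the second and third tests is 84 - 36 = 48 days. It spans the whole washout and essentially all of Period 2.

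**Table against text at Period 2.** Study Procedures places chemistry and ECG before treatment starts in each phase. The table marks both at Screening, Day 36 and Day 84, and neither on Day 50. The pregnancy-test row carries the same three marks. The text does not name the pregnancy test, so this is no direct contradiction for that row. It does show that pre-treatment checks were meant for each phase and that the table omits them at Period 2.

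**End of contact against the contraception commitment.** The text gives 5 weeks per arm (35 days), but the dose steps under Investigational Product add to 7 + 7 + 23 = 37 days. The first Period 2 dose could be taken on the dispensing day or the day after. Last dose = first dose + duration - 1.

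| Duration | First dose | Last dose | Days to Day 91 call | Last dose + 30 | Days after last contact |
|---|---|---|---|---|---|
| 35 | Day 50 | Day 84 | 7 | Day 114 | 23 |
| 35 | Day 51 | Day 85 | 6 | Day 115 | 24 |
| 37 | Day 50 | Day 86 | 5 | Day 116 | 25 |
| 37 | Day 51 | Day 87 | 4 | Day 117 | 26 |

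The Day 84 test therefore falls on the last dosing day or up to three days before it.

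**Who is exposed to ecopipam.** The cross-over gives each participant ecopipam in one period only. Period 2 ecopipam goes to placebo-first participants. For ecopipam-first participants, the last active dose falls between Day 34 (0 + 35 - 1) and Day 37 (1 + 37 - 1). Thirty days later is Day 64 to 67, before contact ends. As far as ecopipam exposure goes, both gaps therefore concern the placebo-first sequence. The withdrawal rule and the contraception commitment apply to everyone, and staff are blinded to sequence.

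**The case against.** Several stronger readings are tempting, and the documents do not support them.

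- *That no pregnancy test precedes Period 2 dispensing.* The Day 36 test does, by 14 days. A pregnancy detectable then would be found before Period 2 drug is handed out.
- *That a pregnancy exposed in Period 1 could be re-exposed.* A participant given ecopipam in Period 1 receives placebo in Period 2. The remaining case is a first exposure in a placebo-first participant.
- *That the withdrawal rule cannot act until the whole arm has been dosed.* Adverse events and medications are reviewed on Days 43, 50, 57, 65, 72 and 84, and participants are told to report concerns on calls. A recognised pregnancy could trigger withdrawal at any of these. Only scheduled testing is missing.
- *That the 30 days are a reproductive risk or monitoring window which the schedule contradicts.* The protocol states a contraception commitment and nothing more, and its risk section names no reproductive risk. A duty that outlasts contact is not in itself a contradiction. The stated half-life is 8 to 15 hours, so 7 days (168 hours) is 168/15 = 11 to 168/8 = 21 half-lives. Uncovered calendar days are therefore not a measure of exposure.
- *That birth defects cannot be reported after Day 91.* The serious adverse event definition sets no such cut-off. A call at about Day 114 could not observe a birth outcome in any case. The consent form and Investigator Brochure are not available here and may carry pregnancy-reporting instructions.

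The Visit 1 gap may also be zero, because screening can take place on Day 0 and Investigational Product counts baseline and screening as one visit. These objections narrow the point considerably. They do not supply a test between Day 36 and Day 84, or a scheduled enquiry after Day 91.

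**Conclusion.** The point holds as a modest gap in safety scheduling. Pregnancy is both an exclusion and a reason for withdrawal. Yet neither dispensing visit carries a test, and the second and third tests are 48 days apart, with Period 2 dispensing 14 days into that interval. Scheduled contact also stops 23 to 26 days before the contraception commitment can end. This part is weaker: it is a loose end to reconcile and not a contradiction.

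The size in participants is unknown. The trial recruits up to 10 people aged from 21, and the number of women of child-bearing potential is not stated and could be small. The day counts rest on visits taking place on their nominal days and on the unresolved 35- or 37-day dosing length. How early a urine test turns positive is not in the documents and is not assumed.

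**What to change.** The sponsor should reconcile the pregnancy-test row with the dispensing days, the exclusion criterion and the withdrawal rule. One way is to mark the existing urine test at the existing Visit 4, before dispensing. That costs one dipstick per woman of child-bearing potential, at most 10 in the trial, and no extra visit. The same edit should settle whether chemistry and ECG belong on Day 50, since text and table disagree. It should also say whether a screening test up to 14 days old is meant to serve for Day 0.

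Separately, the sponsor should reconcile the end of safety contact with the 30-day commitment and state how a pregnancy arising after Day 91, in a participant or a partner, is expected to reach the study team. If the sponsor chose a further call for this, it would be one per participant (10 in all), 23 to 26 days later than the present last contact. The 35- and 37-day dosing lengths must be reconciled first, because the last-dose date depends on them. Which clinical rule applies is for the sponsor to decide.

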Investigational Product

Ecopipam (also known as PSYRX 101 or SCH 39166) hydrochloride is a potent, selective antagonist of human D1 and D5 dopamine receptors. Dopamine is a neurotransmitter in the central nervous system, and its receptors have been classified into two “families” based on their genetic structure: “D1” (including subtypes D1 and D5) and “D2” (including subtypes D2, D3 and D4). D1-receptor super-sensitivity may be a mechanism for the repetitive and compulsive self-injurious behaviors. Ecopipam is a selective antagonist of the D1-receptor family and had been investigated for the symptomatic relief of self-injurious behavior (SIB) in patients with Lesch-Nyhan Disease, Pathological Gambling and Tourette Syndrome. Detailed information about ecopipam development may be found in the Investigator Brochure.

Subjects will be randomized in a double-blind fashion to study drug: ecopipam or matching placebo, supplied by Psyadon Pharmaceutical for study period 1 and 2. Prior to drug dispensation to subjects, subjects will be provided a diary, instructed on daily morning dosing, and asked to return all unused drug and packaging with the diary to the clinic. Subjects will be instructed to report any concerns and/or side effects on contact calls that will occur between study visits.

The double-blind drug assignment code will be maintained in a confidential manner where investigator, study team and patients are unaware of individual treatment assignments. Randomization process must be completed by research personnel not involved in conduct of study visits. Only in the event of a subject related emergency with the specific request to unblind the study drug by the Principal Investigator will the identity of the double-blind drug will be disclosed.

Subjects will be seen six times to complete the study. Arm1 baseline/screening, Arm 1 week 3, Arm 1 week 5, Arm 2 baseline, Arm 2 week 3, Arm 2 week 5. Once daily morning dosing will occur for 5 weeks per arm with weekly dose escalation as the example shows below:

Study Period 1

- Ecopipam or matching placebo 25 mg by mouth for 7 days (week 1), followed by
- Ecopipam or matching placebo 50 mg by mouth for 7 days (week 2), followed by
- Ecopipam or matching placebo 100 mg by mouth for 23 days (weeks 3).
- Wash-out for 2 weeks to allow subjects to switch study arms.

Study Period 2

- Matching placebo or ecopipam 25 mg by mouth for 7 days (week 7), followed by

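### The schedule of events omits the pre-dose serum chemistry and ECG that the protocol text requires at the start of Period 2 (Visit 4, Day 50)

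*Protocol*

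**What the plan says.** Protocol, Study Procedures, Physical and Neurological Examinations: the tests concerned are "Laboratory assessments of serum chemistry and a 12-lead ECG". As to timing, the text says that these "will be conducted on the first day (before initiating treatment) and the last day of treatment of each crossover phase". The sentence covers both treatments.

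Protocol, Schedule of Events: the row "Serum Chemistry" and the ECG row carry identical marks, at the column headed "Baseline Screening Visit: Day -14 to 0", at Visit 3 (Day 36) and at Visit 6 (Day 84). Both rows are blank at Visit 1 (Day 0) and Visit 4 (Day 50), the two visits at which study drug is dispensed.

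Protocol, Investigational Product: the visits are listed as "Arm1 baseline/screening, Arm 1 week 3, Arm 1 week 5, Arm 2 baseline", followed by the two later Arm 2 visits. The periods are separated by "Wash-out for 2 weeks to allow subjects to switch study arms".

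Protocol, Safety Monitoring of Subjects: AST or ALT at three times the upper limit of normal leads to withdrawal, and so do "kidney function changes from baseline as determined by BUN/Creatinine". The sentence does not say which sample is the baseline.

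**The concern.** The text and the table give different instructions for the same two safety tests, and nothing in the protocol says which prevails. Timing of safety samples is fixed in the protocol itself, so this is not a detail left to an analysis plan.

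If the table is followed, Period 2 dosing starts with no chemistry or ECG after the washout. Two things are lost:

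- **A safety check.** A Day 36 abnormality that did not reach a withdrawal limit is not rechecked before the subject starts the second treatment, which may be ecopipam.
- **Attribution.** The Study Synopsis gives gross tolerability as a purpose of the study and says that carry-over is unknown. Without an off-drug value between the periods, a change at both Day 36 and Day 84 cannot be read as one that persisted or as one that resolved and returned. A change first seen at Day 84 cannot be dated to before or after the first Period 2 dose.

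**Working it through.** The protocol gives no statistical figure on this point. The check compares the text with the table and then does simple date arithmetic.

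**Step 1: time points required and scheduled.** The text requires 2 phases × 2 times (first day before dosing, last day) = 4. Each schedule row has 13 visit cells, and reading them against the 13 column heads gives:

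| Time point | Text | Schedule |
|---|---|---|
| Period 1, before dosing | required on the first day | screening visit (Day -14 to 0); blank at Visit 1 |
| Period 1, last day | required | Visit 3, Day 36 |
| Period 2, before dosing | required on the first day | **blank at Visit 4, Day 50** |
| Period 2, last day | required | Visit 6, Day 84 |

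The columns are not misaligned. Read the same way, the drug dispensation row falls on Days 0 and 50, and the RLS rating scale row falls on Days 0, 15, 36, 50, 65 and 84, as expected.

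**Step 2: size of the shortfall.** 4 − 3 = 1 time point per subject. With 10 subjects that is 10 chemistry samples and 10 ECGs. If screening is not accepted as the Period 1 first-day sample and falls before Day 0, the shortfall is 2 per subject, or 20 of each.

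**Step 3: intervals under the schedule as marked.**

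- Last sample to first Period 2 dose: 50 − 36 = 14 days. That last sample is an end-of-treatment sample.
- Day 36 sample to Day 84 sample: 84 − 36 = 48 days.
- Screening sample to Day 84: 84 − 0 = 84 days to 84 + 14 = 98 days.

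**Step 4: would Day 50 be an off-drug value?** The background section gives a half-life of 8 to 15 hours. The washout is 14 × 24 = 336 hours. 336 / 15 = 22.4 and 336 / 8 = 42, so about 22 to 42 half-lives pass. A Day 50 sample would be free of drug, which is what makes it useful as a reference.

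**Step 5: who is affected.** Subjects whose Day 36 values reach a withdrawal limit do not enter Period 2. The gap therefore matters for laboratory changes below those limits and for ECG changes, for which Safety Monitoring of Subjects sets no withdrawal limit.

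**The case against.** **Drug is gone by Day 50.** After at least 22 half-lives, a direct drug effect should have faded. That is fair, and it lowers the risk. But clearance of the drug does not show that a laboratory or ECG change has recovered, and the protocol's own text asks for the sample.

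**Other monitoring exists.** Physical examination, vital signs and adverse events are scheduled at Day 50, and there is a call "1 week after withdrawal) of each arm". This stands, but none of it would show a symptomless change in chemistry or ECG.

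**The team may follow the text.** The sponsor is also the investigator, so the intent may be well understood. If so, correcting the table costs nothing beyond what is already planned.

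**Stronger readings that the protocol does not support.**

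- A reader might infer that Period 1 also lacks a pre-dose sample, because Day 0 is blank. It does not. The screening column carries both tests, its window includes Day 0, and Investigational Product merges screening with the Arm 1 baseline. At most the sample is up to 14 days early.
- A reader might infer that the renal rule has no usable baseline at Day 84. The screening visit is labelled as the baseline and includes chemistry, so the rule can be applied. The remaining ambiguity is with the Arm 2 baseline visit, which has no chemistry.
- A reader might infer that screening and Day 36 are rival baselines that could reverse a Day 84 withdrawal. Nowhere is Day 36 called a baseline, and most subjects with a marked renal rise at Day 36 would already have been withdrawn.
- The long interval to Day 84 is only partly an inconsistency. The text asks for nothing between Day 50 and Day 84 either.

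**Conclusion.** The point holds for Day 50. The text requires four chemistry and ECG time points and the schedule provides three. The missing one is the Period 2 pre-dose sample, and no other part of the protocol supplies it. The size is one sample of each kind per subject, or 10 of each if all 10 subjects reach Visit 4. This count takes the screening sample as the Period 1 pre-dose sample, which the visit list supports.

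The consequences are a missed check of unresolved sub-threshold changes before Period 2, and weaker attribution of Day 84 findings. The protocol gives no expected frequency for such changes, so none is estimated here. The undefined baseline in the renal rule is a small ambiguity that can be settled in the same edit. The content of the renal trigger is a separate clinical matter and need not change. Severity is low, and confidence in the inconsistency is high.

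**What to change.** 1. **Schedule of Events:** mark serum chemistry and 12-lead ECG at Visit 4 (Day 50), pre-dose, and state that the results are reviewed before the first Period 2 dose.
2. **Physical and Neurological Examinations:** state that the screening sample and ECG serve as the Period 1 pre-dose assessment, or require them on Day 0.
3. **Safety Monitoring of Subjects:** state that the baseline in the renal withdrawal rule is that Period 1 pre-treatment sample, and that Day 50 is the reference for attributing a later change to Period 2.

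**Cost:** one chemistry draw and one ECG per subject beyond the current table (10 of each in 10 subjects), all already required by the text. If the laboratory does not report on the same day, the first Period 2 dose may move to the next morning. Accepting screening as the Period 1 sample costs nothing, and doing the screening tests on Day 0 adds no further tests. If an earlier screening sample is kept and the tests are repeated on Day 0, that adds at most another 10 of each.
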